12.4 Response Criteria

Evaluation of Target Lesions

Complete Response (CR): Disappearance of all target lesions

Partial Response (PR): At least a 30% decrease in the sum of the longest diameter (LD) of target lesions, taking as reference the baseline sum LD

Progressive Disease (PD): At least a 20% increase in the sum of the LD of target lesions, taking as reference the smallest sum LD recorded since the treatment started or the appearance of one or more new lesions

Stable Disease (SD): Neither sufficient shrinkage to qualify for PR nor sufficient increase to qualify for PD, taking as reference the smallest sum LD since the treatment started

Evaluation of Non-target Lesions

Complete Response (CR): Disappearance of all non-target lesions and normalization of tumor marker level Incomplete Response/ Stable Disease (SD): Persistence of one or more non-target lesion(s) or/and maintenance of tumor marker level above the normal limits

[figure not shown]
Progressive Disease (PD): Appearance of one or more new lesions and/or unequivocal progression of existing non-target lesions. Although a clear progression of "nontarget" lesions only is exceptional, in such circumstances, the opinion of the treating physician should prevail, and the progression status should be confirmed at a later time by the review panel (or study chair).

Note: If tumor markers are initially above the upper normal limit, they must normalize for a patient to be considered in complete clinical response.

Evaluation of Best Overall Response

The best overall response is the best response recorded from the start of the treatment until disease progression/recurrence (taking as reference for progressive disease the smallest measurements recorded since the treatment started). The patient's best response assignment will depend on the achievement of both measurement and confirmation criteria.

Target Lesions	Non-target Lesions	New Lesions	Overall Response
CR	CR	No	CR
CR	Incomplete	No	PR
	response/SD		
PR	Non-PD	No	PR
SD	Non-PD	No	SD
PD	Any	Yes or No	PD
Any	PD	Yes or No	PD
Any	Any	Yes	PD

Patients with a global deterioration of health status requiring discontinuation of treatment without objective evidence of disease progression at that time should be classified as having "symptomatic deterioration." Every effort should be made to document the objective progression, even after discontinuation of treatment.

In some circumstances, it may be difficult to distinguish residual disease from normal tissue. When the evaluation of complete response depends on this determination, it is recommended that the residual lesion be investigated (fine needle aspirate/biopsy) before confirming the complete response status.

Non-measurable disease: Patients with non-measurable disease (ie, bone only disease) will be evaluated only as either stable disease or progressive disease.

13.0 CRITERIA FOR REMOVAL FROM STUDY

Patients will be removed from the study if any of the following conditions apply:

- intercurrent illness which would in the judgment of the investigator effect assessments of clinical status to a significant degree or require discontinuation of drug;
- unacceptable toxicity;
- progressive disease;
- request by the patient to withdraw;
- patient non-compliance with protocol;
- irradiation of an indicator lesion during the trial;
- if at the discretion of the investigator continued treatment would be harmful or ineffective.

14.0 BIOSTATISTICS

This is a multicenter, open-label, phase II study to evaluate the efficacy of bicalutamide administered orally daily to patients with ER(-)/PR(-)/AR(+) metastatic breast cancer. The primary endpoint of this trial is the response rate (RR), defined as the total number of patients who demonstrate a complete response (CR), partial response (PR) or stable disease (SD) (after 6 months from the first day of treatment) divided by the total number of patients treated. Upon

IRB#: 07-022A(13)

completion of the study, the RR will be estimated via the observed response rate and an exact confidence interval will be constructed. The response rate for patients with only measurable disease will be reported separately as the number of patients who demonstrate a CR, PR or SD >6months divided by the number of patients with measurable disease treated with bicalutamide. For this trial, a target response rate of 20% or higher is considered promising. A target response rate below 5% is considered unacceptable.

This study is designed as a single-stage, phase II which requires a total of 28 patients. If 4 or more patients have a CR, PR or SD after 6 months from the first day of treatment, bicalutamide will be considered feasible and will merit further clinical study. With 28 patients, this design discriminates between true response rates of $\leq 5\%$ and $\geq 20\%$ at a Type I error of 5% and a Type II error of 16%.

Secondary objectives of this study include estimating median progression-free survival at 6 months and describing the rate of selected non-hematologic and hematologic toxicities. Progression-free survival will be estimated by the Kaplan-Meier method. Selected toxicities will be described by frequency and grade, by cycle and overall cycles, with the maximum grade over all cycles used as the summary measure per patient. The safety endpoint will also be measured as the percentage of patients who are able to tolerate daily treatment with bicalutamide after a maximum of 2 (50mg) dose reductions from the starting dose of 150mg, for 6 months from the first day of treatment.

Data analysis plan:

Upon completion of the study, response rate will be estimated via the observed response rate and an exact confidence interval will be constructed. Categorical variables (such as toxicities, responses) will be summarized by counts, percentages or contingency tables and confidence intervals. Continuous variables and changes in continuous variables will be summarized by means, medians and standard deviations. For the correlative studies, analysis is exploratory in nature and hypothesis generating. The relationship between immunohistochemical expression and response will be explored using graphical methods. Similarly, changes in hormone levels over time during treatment with bicalutamide will be described.

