2.3 Secondary Objectives

The secondary objectives of this study are to:

- Estimate the progression-free survival (PFS) at 6 months for patients with ER(-)/PR(-)/AR(+) metastatic breast cancer
- Evaluate the safety of bicalutamide for patients with ER(-)/PR(-)/AR(+) metastatic breast cancer.
- Perform correlative studies including:
 - Monitoring of changes in estradiol, total and free testosterone and sex-hormone binding globulin in response to androgen blockade in women with breast cancer
 - Immunohistochemical analysis of tissue including cytokeratins 5/6 and 17, SPDEF, ALCAM, ERBB2, FGFR4 and PSA
 - Collection and storage of AR+ paraffin embedded tissue samples from primary or metastatic site, if available. These samples will be used to further investigate the biology of AR+ breast cancer (ie, by building a tissue microarray).

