For safety and tolerability, the most common adverse events reported with bicalutamide were breast pain (73.6%) and gynecomastia (68.8%). Symptoms were reported as mild to moderate in over 90% of cases. Symptoms typically developed within the first 6 to 9 months of treatment. Other adverse events were infrequent and included impotence (9.3% with bicalutamide and 6.5% with standard care alone), decreased libido (3.6% and 1.2%, respectively), hotflushes (9.2% and 5.4% respectively), and abnormal liver function tests (3.1% and 1.7%, respectively). Withdrawal rates from the study due to adverse events were 29.3% with bicalutamide and 10.0% with standard care alone. Withdrawal rates secondary to breast pain and/or gynecomastia were 16.8% and 0.7% respectively. In the bicalutamide group, fewer patients died from prostate cancer than those receiving standard care alone (6.4% vs 7.5%). Deaths from heart failure and gastrointestinal carcinoma were higher in the bicalutamide group, though there were no consistent patterns to suggest that these were due to drug toxicity.

IRB#: 07-022A(13)

[figure not shown]
10

The most common adverse events and causes of death, as number (%) of patients ¹⁰					
Variable	Bicalutamide 150 mg + Standard care alone				
	standard care				
	N=4022	N=4031			
Adverse Event					
Breast pain	2962 (73.6%)	308 (7.6%)			
Gynecomastia	2766 (68.8%)	334 (8.3%)			
Pharyngitis	448 (11.1%)	470 (11.7%)			
Asthenia	442 (11.0%)	315 (7.8%)			
Back pain	420 (10.4%)	490 (12.2%)			
Rash	404 (10.0%)	337 (8.4%)			
Constipation	380 (9.4%)	314 (7.8%)			
Impotence	375 (9.3%)	263 (6.5%)			
Hot flushes	370 (9.2%)	216 (5.4%)			
Arthralgia	355 (8.8%)	405 (10.0%)			
Cause of death					
Prostate cancer	257 (6.4%)	302 (7.5%)			
Myocardial infarction	81 (2.0%)	76 (1.9%)			
Cause unknown	68 (1.7%)	63 (1.6%)			
Gastrointestinal carcinoma	54 (1.3%)	38 (0.9%)			
Heart failure	49 (1.2%)	25 (0.6%)			
Cerebrovascular accident	47 (1.2%)	45 (1.1%)			
Lung carcinoma	44 (1.1%)	47 (1.2%)			
Heart arrest	37 (0.9%)	33 (0.8%)			
Pneumonia	34 (0.8%)	45 (1.1%)			

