10.0 EVALUATION DURING TREATMENT/INTERVENTION

Day 0 and every 4 weeks (+/- 5 days), the following clinical and laboratory assessments must be done prior to continuation of treatment with bicalutamide:

- History and physical examination, including:
 - Vital signs
 - ECOG performance status
 - o Weight
 - Concomitant medications
- Laboratory assessments, including: (screening labs can be used as Day 0 labs)
 - CBC with differential and platelet count
 - Comprehensive metabolic panel (Na, K, Cl, CO2, BUN, Creatinine, Ca, Glucose, Total Protein, Albumin, Alkaline Phosphatase, Total Bilirubin, AST and ALT)
- Adverse Event Evaluation (toxicity assessment using the NCI CTC version 3)
- Blood for correlative study of hormonal levels including estradiol, total testosterone, free testosterone, and sex-hormone binding globulin will be performed at baseline, after Cycle #1 and at the end of study. (See further description below)

Every 12 weeks (+/- two weeks), tumor assessments will be performed. Patients with measurable disease will be evaluated for complete response (CR), partial response (PR), stable disease (SD) or progressive disease (PD) using RECIST criteria, using the same modality of imaging performed at baseline. Patients with non-measurable disease will be evaluated for either stable disease or progressive disease. Responders and stable disease patients will continue on study unless they develop unacceptable toxicity. Progressive disease or unacceptable toxicity (after a maximum of two dose reductions) will be the criteria for treatment failure and discontinuation from the study.

Response assessment will include:

- Radiologic scans of disease sites (e.g. CT scan of chest, abdomen and pelvis and PET or bone scan if there are bone lesions identified on pre-study bone imaging)
- Measurement of all target lesions that are followed by physical examination
- Patients achieving a CR or PR must have confirmation of response at least 4 weeks following the initial response determination.
- End-of-Study (EOS) Evaluation: At the time patients are removed from study, laboratory and clinical evaluations to assess adverse events (AEs) will be performed. Serum hormone panel including estradiol, free and total testosterone and serum hormone binding globulin will be collected. Radiologic studies for antitumor response will be repeated if they have not been performed within the previous 28 days.

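### PFS has no event or censoring rule and no tumour follow-up after the end-of-study evaluation, so 6-month PFS can be biased upward when patients leave without documented progression

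*Combined protocol and SAP*

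**What the plan says.** **The quantity.** The first secondary objective in section 2.3 reads "Estimate the progression-free survival (PFS) at 6 months for patients with" ER(-)/PR(-)/AR(+) metastatic disease. Section 14.0 words the same objective as a median PFS at 6 months, which is a different quantity. The only analysis statement is "Progression-free survival will be estimated by the Kaplan-Meier method". Neither section defines the event, says whether death counts, or gives a censoring rule.

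**Removal.** Section 13.0 lists seven reasons for removal, of which one is progression. The others are intercurrent illness, unacceptable toxicity, patient request, non-compliance, irradiation of an indicator lesion, and "if at the discretion of the investigator continued treatment would be harmful or ineffective".

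**Assessment at and after removal.** Section 10.0 says "At the time patients are removed from study, laboratory and clinical evaluations to assess adverse events (AEs) will be performed", and has imaging repeated unless it was done in the previous 28 days. The Time and Events Schedule marks CT and PET or bone scan at study termination. Its only later column, AE resolution, contains no tumour assessment. Section 12.4 addresses "Patients with a global deterioration of health status requiring discontinuation of treatment without objective evidence of disease progression at that time" and asks for every effort to document progression afterwards, but sets no schedule and covers only that group.

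**Later deaths.** The section on physician reporting of adverse events (17.2.1) follows patients to the end of study or 30 days after treatment, whichever is longer. After withdrawal, section 17.2.5 asks for notice of deaths or SAEs that may reasonably be related to study medication, and does not oblige investigators to look for events. The data submission chart in section 16.1.3 ends at the off-study visit.

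**The primary endpoint.** In section 14.0 the rate divides by all patients treated, so a patient removed before 6 months stays in the denominator as a non-success.

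**The concern.** Kaplan-Meier estimation treats a censored patient as having the same outlook as those still under observation at that time. Some exits in this protocol break that assumption. A patient whose treatment the investigator judges ineffective, or who stops for global deterioration, is probably closer to progression than one who continues. A scan up to 28 days old satisfies the end-of-study requirement, so worsening since that scan need not be imaged. If such patients are censored at exit and their later progression or death is not collected, 6-month PFS is biased upward.

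This matters because the primary endpoint (CR, PR or SD at 6 months over all treated) is close to being progression-free at 6 months with removals counted as failures. The two 6-month figures will be read side by side, and they differ mainly through a censoring rule that the plan does not state.

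**Working it through.** **1. The plan's own figures.** Section 14.0 describes a design "which requires a total of 28 patients", with the rule "If 4 or more patients have a CR, PR or SD after 6 months from the first day of treatment". The exact binomial gives P(X ≥ 4 | n = 28, p = 0.05) = 0.049 and P(X ≤ 3 | n = 28, p = 0.20) = 0.160, matching the stated 5% and 16%. The smallest success is 4/28 = 14.3%, exact 95% interval 4.0% to 32.7%. The plan gives no figure for PFS.

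**2. Number of removals (an assumption).** The documents give no rate for this trial. Section 3.2 gives adverse-event withdrawal in men: 6% in the M0/M1 prostate cancer trials, while in the early prostate cancer program "Withdrawal rates from the study due to adverse events were 29.3% with bicalutamide". Then 28 × 0.06 = 1.7 and 28 × 0.293 = 8.2, so about 2 to 8 patients.

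**3. Kaplan-Meier at 6 months.** Hold the primary result at 4 of 28 and place scans at weeks 12 and 24. Let P be the progressions found at week 12 and w the patients censored without progression between the two scans. Then

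S = ((28 − P)/28) × (4/(28 − P − w)).

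If all w leave before the first event, S = 4/(28 − w). If every progression is found at week 12, S = (4 + w)/28. These are the lower and upper limits.

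| w | All leave before first event | Intermediate cases | All progressions at week 12 |
|---|---|---|---|
| 2 | 4/26 = 15.4% | P = 12: (16/28)(4/14) = 16.3%; P = 18: (10/28)(4/8) = 17.9% | 6/28 = 21.4% |
| 4 | 4/24 = 16.7% | P = 16: (12/28)(4/8) = 21.4% | 8/28 = 28.6% |
| 8 | 4/20 = 20.0% | P = 8: (20/28)(4/12) = 23.8%; P = 12: (16/28)(4/8) = 28.6% | 12/28 = 42.9% |

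**4. How much of the gap is bias.** With complete follow-up, the estimate would be (4 + j)/28, where j is the number of removed patients still progression-free at 6 months. Kaplan-Meier in effect supplies its own j. With w = 2 and P = 18 it gives 5/28, crediting 1 of the 2. With w = 8 and P = 12 it gives 8/28, crediting 4 of the 8. If those fractions are right, there is no bias. If all the removed patients progress or die by 6 months (j = 0), the whole gap above 14.3% is bias: 3.6 points in the first case (17.9 − 14.3) and 14.3 in the second (28.6 − 14.3). The documents do not say where between these the truth lies.

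**5. If withdrawal is unrelated to prognosis.** With withdrawal probability d by 6 months, the ratio of Kaplan-Meier PFS to the primary rate is about 1/(1 − d): 1/0.94 = 1.06 at 6% and 1/0.707 = 1.41 at 29.3%. A large-sample simulation with exponential progression and withdrawal, true 6-month PFS of 20%, and an end-of-study scan that detects any progression present gives ratios of 1.04 and 1.27.

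**The case against.** **The end-of-study scan.** A reader might infer that removed patients get no further tumour assessment. The documents do not support that. Imaging is required at removal unless done in the previous 28 days, and section 12.4 asks for progression to be documented after symptomatic deterioration. The gap begins only after the end-of-study evaluation.

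**Censoring is inferred.** The plan does not say these patients will be censored. This is correct. The documented defect is the missing rule; censoring is what ordinary practice would supply.

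**Size.** A reader might infer that PFS can reach about twice the primary rate. Twice is neither typical nor a limit. It depends on how exits and progressions are timed, and the same formula runs from 1.1 times (15.4/14.3) to 3.0 times (42.9/14.3). The 29.3% comes from localized or locally advanced disease at a median follow-up of 7.4 years, and 16.8 points of it were for breast pain or gynecomastia. Section 3.2 says those effects were reported less often in metastatic patients, so 6% is the nearer setting, though still in men. At 2 removals the typical shift is at most one patient in 28, well inside the interval for 4/28.

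**Difference or bias.** The primary rate counts removal as failure and Kaplan-Meier does not, so a gap between them is not itself an error. This stands. Only exits linked to prognosis cause bias, and adverse-event withdrawal rates do not measure those.

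**Consequences.** A reader might set PFS against the 20% mark. That mark belongs to the response rate; PFS has no threshold.

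None of this supplies the missing definition or recovers later progressions and deaths.

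**Conclusion.** The point holds as a cheap improvement to a secondary, descriptive endpoint. As written, the plan leaves PFS undefined and can lose progressions and deaths after the end-of-study evaluation. Where removal signals imminent progression, 6-month PFS is biased upward by an amount the documents cannot fix.

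For illustration, against 14.3% on the primary endpoint, Kaplan-Meier PFS is about 15-18% with 2 removals under typical timing and 20% or more with 8. These figures assume exactly 4 successes, scans at weeks 12 and 24, censoring at exit, and withdrawal rates carried over from men with prostate cancer. They bound the combined effect of the different estimand and any bias, and do not measure bias alone. The 4-of-28 decision and its error rates are unaffected.

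**What to change.** In sections 10.0, 13.0 and 14.0:

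- For patients removed without progression who still consent, collect progression status (routine-care scan reports suffice), date of death, and start of any new anticancer therapy, until progression, death or 6 months from first dose.
- Define PFS events as progression or death from any cause, and state the censoring rule. State how new anticancer therapy is handled, because later scans would otherwise partly reflect that treatment.
- Report the number censored before 6 months, with reasons, beside the PFS estimate.
- Count removal as ineffective and symptomatic deterioration as events in a sensitivity analysis only. Section 12.4 keeps symptomatic deterioration apart from objective progression, and a judgement of ineffectiveness is subjective in an open-label trial. Counting every removal as an event would add little: in the model above it returns 4/28, the primary rate.
- Reconcile PFS at 6 months (section 2.3) with the median wording in section 14.0.

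The cost is a short amendment, record collection for up to a few months in perhaps 2 to 8 patients, and a possibly slightly lower PFS estimate. Treatment does not change.

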15.0 RESEARCH PARTICIPANT REGISTRATION AND RANDOMIZATION PROCEDURES

15.1 Research Participant Registration

Confirm eligibility as defined in the section entitled Criteria for Patient/Subject Eligibility.

Obtain informed consent, by following procedures defined in section entitled Informed Consent Procedures.

During the registration process registering individuals will be required to complete a protocol specific Eligibility Checklist.

IRB#: 07-022A(13)

All participants must be registered through the Protocol Participant Registration (PPR) Office at Memorial Sloan-Kettering Cancer Center. PPR is available Monday through Friday from 8:30am – 5:30pm at [contact]. The PPR fax numbers are [contact] and [contact]. Registrations can be phoned in or faxed. The completed signature page of the written consent/verbal script and a completed Eligibility Checklist must be faxed to PPR.

15.2 For Participating Centers:

Central registration for this study will take place at Memorial Sloan Kettering Cancer Center (MSKCC).

To complete registration and enroll a participant from another institution, the study staff at that site must contact the designated research staff at MSKCC to notify him/her of the participant registration. The site staff then needs to fax registration/eligibility documents to the 07-022 Research Staff at MSKCC [contact].

The following documents must be sent for each enrollment **within 24 hours** of the informed consent form being signed:

- The completed or partially completed MSKCC eligibility checklist
- The signed informed consent and HIPAA Authorization form (Research Authorization)
- Supporting source documentation for eligibility questions (laboratory results, pathology report, radiology reports, MD notes, physical exam sheets, medical history, prior treatment records, and EKG report).

Upon receipt, the research staff at Memorial Sloan Kettering Cancer Center will conduct an interim review of all documents. If the eligibility checklist is not complete, the patient will be registered PENDING and the site is responsible for sending a completed form within 30 days of the consent.

If the eligibility checklist is complete, participant meets all criteria, all source documentation is received, the participating site IRB has granted approval for the protocol, and the site is in good standing with MSKCC, the MSKCC research staff will send the completed registration documents to the MSKCC Protocol Participant Registration (PPR) Office to be enrolled as stated in section 15.1. The participant will be registered.

Once eligibility has been established and the participant is registered, the participant will be assigned an MSKCC Clinical Research Database (CRDB) number (protocol participant number). This number is unique to the participant and must be written on all data and correspondence for the participant. This protocol participant number will be relayed back to study staff at the registering site via e-mail and will serve as the enrollment confirmation.

